**Figure 5 Study Schema**

##### 3.1.1 Dose Escalation Phase

- Approximately 12 evaluable patients will be enrolled. The actual number of patients will depend on the occurrence of dose-limiting toxicities (DLTs) as well as the MTD level reached in this trial.
- The dose levels to be investigated are 3 mg and 5 mg QD, 3 weeks on/1 week off.
- Six DLT-evaluable patients will be enrolled in the phase and will be treated with fruquintinib 3 mg QD (3 weeks on/1 week off) orally. If no more than 1 DLT occurs during the DLT observational window (ie, from Days 1-28 in Cycle 1) among the 6 patients, the trial will continue to enroll another 6 patients in the next dose cohort in which fruquintinib 5 mg QD (3 weeks on/1 week off) will be tested.
- Safety monitoring and evaluation for the Dose Escalation phase will be carried out by the Safety Review Committee (SRC). Additional information about the SRC is provided in [Section 3.4](#).

- If no more than 1 patient at the dose level of 5 mg QD experiences a DLT, the dose escalation phase is completed and the expansion phase of the study will be conducted.
- Upon completion of the dose escalation/ phase, the SRC will review the aggregated safety and PK data and then select a fruquintinib dose as the RP2D for the expansion phase of the trial.
- Blood samples for PK assay will be collected in Cycle 1 at the following time points: pre-dose (within 10 minutes), 1, 2, 4, 8, and 24 hours post dose on Days 1, 14 and 21.
- Prior to confirmation of a DLT, if a patient has received any prophylactic medical intervention or missed 4 or more fruquintinib doses during the DLT observational window, the patient is not DLT evaluable and will be replaced.
- If a patient does not meet the definition of DLT evaluable patient criterion during the DLT observation period, the patient will be replaced.
- Patients who have completed the DLT observation period (Days 1-28, Cycle 1) and are deemed to be benefiting from the fruquintinib treatment at the investigator's discretion may continue the fruquintinib treatment until disease progression, death, intolerable toxicity, or at investigator's discretion that the patient can no longer benefit from the study drug.
- Please see [Appendix A](#) for the Schedule of Events and Section 5.2 for the dose modification instructions.
- Patients will be followed until death or study completion.

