### **6.3.4 Cardiac Monitoring**

Left ventricular ejection fraction (LVEF) assessed via echocardiogram and 12-lead ECGs

are required to be performed as scheduled; ECG shall be performed pre-dose and at 3 hours ( $\pm$  15 minutes) post fruquintinib dose on Days 1 and 15 in Cycle 1. ECG will be conducted on Day 1 of each cycle from Cycle 2 and onward. QTcF interval should be calculated and be closely monitored. See [Appendix A](#). MUGAs are permitted if echocardiograms cannot be performed.

Test results will be reviewed by the investigator to determine patient eligibility at screening. Additional tests and other cardiac monitoring should be performed as clinically indicated during the study.

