**Appendix A Study Schedule of Events**

Date Procedure	Treatment 											Treatment Completion 	Follow-up
	Screening		Cycle 1				Cycle 2-3		Cycle 4 and onwards				
	Day -28 to Day -1	Day -7 to Day -1	Day 1	Day 8 (±1d)	Day 15 (±1d)	Day 22 (±1d)	Day 1 (±3d)	Day 15 (±3d)	Day 1 of each subsequent cycle (±3d)				
Informed consent 	X												
Tumor assessment (Dose Escalation, Expansion Cohorts C, D, E)	X		Screening, then every 8 (±1) weeks thereafter ( eg C3D1, C5D1, C7D1, etc.)								X 		
Tumor assessment (Dose Expansion Cohorts A and B only)	X		Screening, C2D1, C3D1 C4D1, and every 8 (±1) weeks thereafter (eg C6D1, C8D1, C10D1, etc.)								X 		
Medical history, demographics	X												
Concomitant medication 	X	X	X	X	X	X	X	X	X	X	X	X	
ECOG performance status		X	X		X		X	X	X	X	X	X	
Vital signs 		X	X	X	X	X	X	X	X	X	X	X	
Complete physical examination 		X											
Limited physical examination 			X	X	X	X	X	X	X	X	X	X	
Height	X												
Hematology 		X		X	X	X	X	X	X	X	X	X	

Date Procedure	Screening		Treatment 							Treatment Completion 	Follow-up
			Cycle 1				Cycle 2-3		Cycle 4 and onwards		
	Day -28 to Day -1	Day -7 to Day -1	Day 1	Day 8 (±1d)	Day 15 (±1d)	Day 22 (±1d)	Day 1 (±3d)	Day 15 (±3d)	Day 1 of each subsequent cycle (±3d)	30 (±7) days after permanent treatment discontinuation	Every 12 (±2) weeks from Treatment Completion Visit
Coagulation assay (aPTT, INR)		X		X	X	X	X	X	X	X	
Chemistry panel 		X		X	X	X	X	X	X	X	
Urinalysis 		X		X	X	X	X	X	X	X	
Echocardiogram 	X		X (Every 12 weeks ± 1 week after the first dose)							X	
Thyroid function test 	X						X		X	X	
Serum pregnancy tests 		X								X	
Urine pregnancy tests 							X		X		
Specific tumor markers  Dose Escalation, Expansion Cohorts C, D, E)	X		Screening, then every 8 (±1) weeks thereafter: C3D1, C5D1, C7D1, etc								
Specific tumor markers  Dose Expansion Cohorts A and B only)			Screening, C2D1, C3D1 C4D1, and every 8 (±1) weeks thereafter								
12-lead electrocardiogram 		X	X		X		X		X	X	
PK plasma sampling			PK samples are being collected on Days 1, 2, 14, and 15 of Cycle 1 for Expansion Cohorts B, C, D, and E. Refer to Appendix D for								

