8. Hematology consists of complete blood count, including red blood cell count, hemoglobin, hematocrit, reticulocyte count, white blood cell count with differential (neutrophils, bands, lymphocytes, eosinophils, monocytes, basophils, and other cells), and platelet count.
9. The chemistry panel includes blood urea nitrogen, creatinine and creatinine clearance, sodium, potassium, chlorine, bicarbonate, calcium, magnesium, phosphorus, glucose, alanine aminotransferase, bilirubin (total), aspartate aminotransferase, alkaline phosphatase, lactate dehydrogenase, total cholesterol, triglycerides, uric acid, protein (total) and albumin.
10. Urinalysis includes pH, glucose, protein, and blood. A 24-hour urine should be collected from all patients with  $>1+$  proteinuria for quantitative test of urine protein during the screening. If protein  $\geq 2+$  during the period of study treatment, a 24-hour urine test should be conducted within 1 week.
11. MUGAs are permitted if echocardiograms cannot be performed.
12. Includes free T3, free T4, and thyroid-stimulating hormone (TSH).
13. Women of childbearing potential will receive a serum pregnancy test during screening and within 30 days after treatment completion, and a urine pregnancy test on Day 1 of each 28-day cycle beginning at Cycle 2. If pregnancy is suspected, additional tests should be completed. In the case of menopausal women, the date of menopause onset should be recorded.
14. CA125 level for patients with ovarian cancer, PSA for patients with prostate cancer, or other tumor markers (as appropriate) should be obtained as clinically indicated or with each tumor assessment.
15. On Days 1 and 15 in Cycle 1, ECG should be performed at pre-dose and at 3 hours ( $\pm 15$  minutes) post-dose (around  $C_{max}$  after single dose and at steady state in order to evaluate concentration-QT relationship for fruquintinib). Untimed ECG will be conducted on Day 1 of each cycle from Cycle 2 and onward.
16. After informed consent, all SAEs and concomitant medications will be collected. After initiation of study drug, all AEs and SAEs will be collected until 30 days following the last dose of study drug or a new treatment of anti-tumor therapy, whichever is earlier. After this period, investigators should report only SAEs that are considered to be related to the study drug.

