**Table D-2 PK Sampling Time Points (Cohort B, C, D, and E of Dose Expansion Phase)**

Visit Cycle	Time Point
Cycle 1, Day 1	Pre-dose ( $\leq 10$ minutes)
	Post-dose 1 hour $\pm\pm(\pm 5$ minutes)
	Post-dose 2 hours $\pm\pm(\pm 15$ minutes)
	Post-dose 4 hours $\pm\pm(\pm 30$ minutes)
	Post-dose 8 hours $\pm\pm(\pm 60$ minutes)
Cycle 1, Day 2	Pre-dose ( $\leq 10$ minutes)
Cycle 1, Day 14	Pre-dose ( $\leq 10$ minutes)
	Post-dose 1 hour $\pm\pm(\pm 5$ minutes)
	Post-dose 2 hours $\pm\pm(\pm 15$ minutes)
	Post-dose 4 hours $\pm\pm(\pm 30$ minutes)
	Post-dose 8 hours $\pm\pm(\pm 60$ minutes)
Cycle1, Day 15	Pre-dose ( $\leq 10$ minutes)

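### The post-dose ECGs meant for the concentration-QT evaluation have no time-matched PK sample; the main gap is at steady state, where the PK profile is on Day 14 and the peak ECG on Day 15

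*Protocol*

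**What the plan says.** **ECGs.** Protocol Section 6.3.4 requires a 12-lead ECG pre-dose and at 3 h (±15 min) "post fruquintinib dose on Days 1 and 15 in Cycle 1". Appendix A, footnote 15, repeats the timing and gives its purpose: readings around Cmax "after single dose and at steady state in order to evaluate concentration-QT relationship for fruquintinib". SAP Appendix 1 reproduces the footnote.

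**PK.** For the later expansion cohorts, Appendix A states: "PK samples are being collected on Days 1, 2, 14, and 15 of Cycle 1 for Expansion Cohorts B, C, D, and E". The matching Appendix D table places post-dose draws at 1, 2, 4 and 8 h on Days 1 and 14. Days 2 and 15 have one pre-dose draw each, which serves as the 24 h point of the day before. For dose escalation, Section 3.1.1 lists pre-dose and "1, 2, 4, 8, and 24 hours post dose on Days 1, 14 and 21". The Appendix D table for escalation and Cohort A agrees, and its Day 21 series has no timed ECG.

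**Analysis.** Protocol Section 8.4 describes non-compartmental PK only. SAP Section 1 leaves PK and pharmacodynamic analyses out of the SAP, and SAP Section 17.5 summarises ECGs descriptively. No concentration-QT method appears in either document.

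**The concern.** A concentration-QT evaluation relates each QT reading to the concentration at the same moment, and the readings near the peak carry most of the information about the upper end of exposure. Here the ECG and PK schedules do not meet at the peak. On Day 1 they differ by about an hour. At steady state they fall on different days, after different doses.

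The only ECGs with a nominally simultaneous PK sample are the pre-dose ones: Day 1, when there is no drug, and Day 15, at trough. At stake is whether the timed ECGs can serve the purpose that footnote 15 gives them without relying on concentrations that were not observed.

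**Working it through.** There is no planned figure to reproduce. The check sets the permitted ECG window against each permitted PK window.

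**Step 1: windows, in minutes after the dose.** The ECG is at 180 ± 15, so 165 to 195.

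| PK draw (tolerance) | Window | Gap to ECG window | Largest possible separation |
|---|---|---|---|
| 1 h (±5) | 55–65 | 165 − 65 = 100 | 195 − 55 = 140 |
| 2 h (±15) | 105–135 | 165 − 135 = 30 | 195 − 105 = 90 |
| 4 h (±30) | 210–270 | 210 − 195 = 15 | 270 − 165 = 105 |
| 8 h (±60) | 420–540 | 420 − 195 = 225 | 540 − 165 = 375 |

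No window overlaps, and the same tolerances apply in both Appendix D tables.

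**Step 2: Day 1.** The 3 h ECG lies between two draws after the same dose, so a concentration can be interpolated. Protocol Section 1.3.1 puts the half-life above 35 h. Elimination is therefore below 0.693/35 = 0.0198 per hour, about 2% per hour. Absorption may add individual variation, but the bracket is fairly tight.

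**Step 3: Day 15.** The only same-day draw is pre-dose, within 10 min before the dose. It precedes the ECG by 165 to 195 + 10 = 205 min and follows the previous day's dose. The Day 14 draws at 2 h and 4 h are nominally 24 + 3 − 2 = 25 h and 24 + 3 − 4 = 23 h before the ECG.

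**Step 4: the Cycle 1 visit window.** Visits may move by ±1 day, so a Day 15 ECG could fall on Day 14. Nothing requires this, and Day 14 has no 3 h draw, so the ECG would then be bracketed as on Day 1.

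**Step 5: how far up the range direct matching reaches.** The inputs come from protocol Table 2, the 5 mg 3-weeks-on/1-week-off column: mean steady-state maximum 383 ng/mL, mean steady-state average 295 ng/mL, DF 43.8%. Table 2 does not define DF. *Assuming* DF = (Cmax − Cmin)/Cav:

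- Cmin = 383 − 0.438 × 295 = 383 − 129 = 254 ng/mL
- 254/383 = 0.66

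Directly matched concentrations would then stop about one third below the mean peak.

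**The case against.** The strongest reply is that the missing concentrations can be recovered. The Day 1 ECG is bracketed by same-day draws. Section 1.3.1 reports that steady state is reached by Day 14 of daily dosing, so the same patient's Day 14 values at the same dose are a reasonable stand-in for Day 15. A population PK model could also predict the concentration at the recorded ECG time. Moreover, concentration-QT is not among the objectives or endpoints in Section 2, where ECG is listed as a safety assessment, and the PK analysis plan is not available here. All of this stands, and it limits the consequence. It does not supply an observed concentration at any peak ECG.

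Three stronger readings are tempting, and the documents do not support them.

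- **The peak exposure range is lost.** Steps 2 and 3 show usable, if unmatched, proxies on both days.
- **Any estimated slope is flattened towards no effect.** That follows from classical random error in concentration. Model-predicted concentrations bring mostly Berkson-type error, with little slope bias in a linear model. Straight-line interpolation that misses a peak between 2 and 4 h would understate concentration and steepen the slope. With no imputation method stated, the direction is unknown.
- **The Table 2 Tmax of 3.6 ± 3.8 h makes borrowed values unreliable.** That is a between-patient spread. It says nothing about one patient's change from Day 14 to Day 15, and a flat profile from a slowly eliminated drug would also scatter Tmax.

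**Conclusion.** The mismatch is confirmed for every cohort, and no tolerance window closes it. By schedule, none of the approximately 128 planned patients has a time-matched post-dose ECG/PK pair on Day 1 or at steady state. The steady-state gap is the more serious, because no same-day post-dose concentration exists. Day 1 is milder.

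The evaluation named in footnote 15 is weakened, not lost: peak concentrations must be interpolated, predicted or borrowed from the previous day. This is worth correcting because it is cheap, but it does not undermine the trial's listed endpoints.

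The conclusion on timing rests only on the schedules. The 254 ng/mL figure rests on an assumed definition of DF and on group means from what appears to be a small cohort (Table 5 lists 7 evaluable patients on this regimen), so it is an indication only. The pre-dose pairs are matched nominally, since footnote 15 sets no time window for the pre-dose ECG.

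**What to change.** Move the steady-state ECG pair (pre-dose and post-dose) from Day 15 to Day 14. On Days 1 and 14, record the post-dose ECG just before an existing PK draw, at either 2 h or 4 h, and leave the PK schedule unchanged.

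**Text to update.** Protocol Section 6.3.4, Appendix A footnote 15 and its copy in SAP Appendix 1. The 3-hour CRF time point that SAP Section 5.2 uses to classify a Day 1 ECG as post-baseline must follow the new time. The C1D15 ECG window in SAP Appendix 4 already runs from Day 2 and includes Day 14, so only labels change there.

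**Cost.** One schedule change in an amendment, with the same number of ECGs and draws. Patients already stay for the 8 h sample on Day 14, and the wait for a post-dose ECG on Day 15 disappears. The downside is that patients already treated keep the old timing. For them, specify before analysis how the concentration at the recorded ECG time will be obtained, and report it as predicted, not observed.

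**Not advised.** Moving the 4 h PK draw to 3 h would leave nothing between 3 and 8 h. A patient whose highest value was at 3 h would then have only the 8 h and 24 h samples after it, against the three points that Section 8.4 requires for the terminal slope. Half-life, clearance and volume, all listed PK secondary endpoints, depend on that slope.

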Revised total sample size of planned enrollment from approximately 50 patients to 128 patients and total sample size of enrollment in the expansion cohorts from approximately 36 to 116 patients.	Section 3.2 Sample Size Section 8.6 Determination of Sample Size

Description and Rationale for Change	Sections
Added justification of sample sizes for Expansion Cohorts B, C, D, and E.	
Changed the primary endpoint for the dose expansion phase to add progression-free survival (PFS) rate at week 12 for Cohorts B and C, PFS rate at week 16 for Cohort D, and PFS rate at week 24 for Cohort E. Added clarification of definition of PFS rate.	Section 2.2.2 Primary Endpoint (dose expansion stage) Section 8.5 Efficacy Analysis
Revised inclusion criterion 4 to have separate inclusion criteria for dose escalation and for expansion cohorts. Added inclusion criteria for Cohorts C, D, and E.	Section 4.1 Inclusion Criteria
Added Inclusion Criterion 5 to specify that hormone receptor positive mBC patients must have progressed on at least two lines of prior systemic therapy, including hormonal therapy or chemotherapy.	Section 4.1 Inclusion Criteria
Added Inclusion Criterion 6 specify that triple-negative breast cancer patients must have progressed on at least one cytotoxic therapy in the metastatic setting, with exception of subjects who progressed within 12 months of adjuvant therapy.	Section 4.1 Inclusion Criteria
Revised Inclusion Criterion 7 (formerly Inclusion Criterion 5) to add that patients may qualify for enrollment in this study if they have bone lesions in the absence of measurable disease	Section 4.1 Inclusion Criteria
Revised Exclusion Criterion 11 to exclude patients with history of a thromboembolic event within 6 months, rather than 12 months, prior to screening.	Section 4.2 Exclusion Criteria
Added an end-of-study definition per regulatory requirements	Section 3.7 End of Study (new section)
Added survival follow-up of patients	Section 3.1.1 Dose Escalation Phase Section 3.1.2 Dose Expansion Phase Appendix A Schedule of Events
Revised tumor assessment schedule and analysis plan to reflect addition of Cohorts C, D, and E	Section 6.4 Efficacy Assessments Section 8.5 Efficacy Analysis Appendix A Schedule of Events
Added that, for cardiac monitoring, MUGAs are permitted if echocardiograms cannot be performed.	Section 6.3.4 Cardiac Monitoring Appendix A Study Schedule of Events
Revised specifications for recording of deaths	Section 7.1.8.5 Death

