### 2.1.4 Secondary Endpoints

- The primary PK parameters include: maximum plasma concentration ( $C_{max}$ ), time to reach maximum concentration ( $T_{max}$ ), terminal half-life ( $t_{1/2}$ ), area under the concentration-time curve in a selected time interval ( $AUC_{0-t}$ ), area under the concentration-time curve in the time interval from 0 to infinity ( $AUC_{0-\infty}$ ), apparent clearance ( $CL/F$ ), apparent volume of distribution ( $V_z/F$ ) during the terminal phase according to  $CL/F/K_e$ , and the accumulation index based on AUC.

- The objective response rate (ORR), disease control rate (DCR), duration of response (DoR), PFS, overall survival (OS) and percentage change in tumor size from baseline according to RECIST Version 1.1.

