Date Procedure	Screening		Treatment 							Treatment Completion 	Follow-up
			Cycle 1				Cycle 2-3		Cycle 4 and onwards		
	Day -28 to Day -1	Day -7 to Day -1	Day 1	Day 8 (±1d)	Day 15 (±1d)	Day 22 (±1d)	Day 1 (±3d)	Day 15 (±3d)	Day 1 of each subsequent cycle (±3d)	30 (±7) days after permanent treatment discontinuation	Every 12 (±2) weeks from Treatment Completion Visit
			specific timepoints								
Adverse event 	X	X	X	X	X	X	X	X	X	X	
Fruquintinib treatment			Once daily, 3 weeks on/ 1 week off								
Survival follow up 											X

Note:

1. A written informed consent form should be obtained prior to any protocol-specific procedure or test. Tests completed within 28 days prior to enrollment can be used for screening and do not need to be repeated (except hematology, coagulation test, clinical chemistry, or urinalysis results).
2. Unless otherwise indicated, the visit window during the treatment period will be ± 3 days (± 1 day during cycle 1).
3. Patients who complete or prematurely discontinue the study need to return to the study site for a follow-up at 30 (±7) days after the decision to discontinue treatment permanently. Ongoing AEs will be followed until the event has resolved to baseline grade, the event is assessed as stable by the investigator, new anti-tumor treatment is initiated, the patient is lost to follow-up, the patient withdraws consent, or when it has been determined that the study treatment or participation is not the cause of the AE.
4. The treatment completion visit tumor assessment can be omitted if treatment ended because of disease progression or the patient had a tumor assessment within 14 days prior to the last dose of study drug.
5. Concomitant medication includes any prescribed or over-the-counter medicines. All medication used by patients within 7 days before screening and 30 days after study treatment completion should be recorded. At each visit, all medication used since the prior visit should be recorded.

6. Vital signs include blood pressure, heart rate, respiratory rate, and temperature. For patient with a baseline history of antihypertensive medications, blood pressure should be monitored at 3 hours ( $\pm 2$  hours) after the daily doses of anti-hypertensive medication.
7. Please refer to Section 6.3.2 for the assessments that should be completed as part of the Complete and Limited Physical Exams.

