17. **For subjects in Expansion Cohorts B, C, D, and E** - Survival follow-up (by telephone) should be performed every 12 ( $\pm$ 2) weeks from the date of the Treatment Completion visit. All subsequent anti-tumor therapy and information about ongoing or unresolved study drug-related SAEs will be collected. For the patients that discontinue the study without PD, all available tumor assessment results during survival follow-up will be recorded in the CRF until confirmation of PD. The date and cause of death should be recorded, if applicable. Patients who withdraw consent are encouraged to be followed for survival. If the patient has clearly expressed his/her refusal to be followed after withdrawal of consent, he/she will terminate the study and no survival follow-up will be performed.

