To investigate DLT, 6 DLT-evaluable patients will be firstly enrolled in the phase and will be treated with fruquintinib 3 mg QD (3 weeks on/ 1 week off) orally. If no more than 1 DLT occurs during the DLT observational window (i.e. from Day 1 – 28 in Cycle 1) among the 6 patients, the trial will continue to enroll another 6 patients in the next dose cohort in which fruquintinib 5 mg QD (3 weeks on / 1 week off) will be tested. Safety monitoring and evaluation for the dose escalation phase will be carried out by the Safety Review Committee (SRC). If no more than 1 patient at the dose level of 5 mg QD experiences a DLT, the dose escalation phase is completed, and the expansion phase of the study will be conducted. Upon the completion of the dose escalation phase, the SRC will review aggregated safety and PK data and then select a fruquintinib dose as the RP2D for the expansion phase of the trial. Prior to confirmation of a DLT, if a patient has received any prophylactic medical intervention or missed 4 or more fruquintinib dose during the DLT observational window, the patient is not DLT evaluable and will be replaced. If a patient does not meet the definition of DLT evaluable patient criterion during the DLT observation period, the patient will be replaced. Patients who have completed the DLT observation period (Days 1 – 28, Cycle 1) and are deemed to be benefiting from the fruquintinib treatment at the investigator’s discretion may continue the fruquintinib treatment until disease progression, death, intolerable toxicity, or at investigator’s discretion that the patient can no longer benefit from the study drug.

Patients will be followed until death or study completion, which is defined as the CRF form “End of Study” is filled.

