2.3. STUDY ENDPOINTS

2.3.1. DOSE ESCALATION PHASE

- Primary Endpoints: The primary endpoint of the dose escalation phase is the incidence of DLT in each cohort.
- Secondary endpoints: The objective response rate (ORR), disease control rate (DCR), duration of response (DoR), and progression free survival (PFS) according to RECIST Version 1.1 (Eisenhauer et al., 2009), overall survival (OS) and percentage change from baseline in tumor size.

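### Protocol and SAP contradict themselves on survival follow-up for dose escalation and Cohort A: the text follows patients to death or study completion, but the schedule gives survival contacts only to Cohorts B–E

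*Protocol*

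**What the plan says.** **OS is an endpoint for these patients.** Protocol 2.1.4 lists "PFS, overall survival (OS) and percentage change in tumor size from baseline according to RECIST Version 1.1" among the escalation secondary endpoints, and SAP 2.3.1 repeats it ("overall survival (OS) and percentage change from baseline in tumor size"). Protocol 2.2.4 lists OS for the expansion phase without excluding any cohort, so Cohort A is included. SAP 16.2 plans Kaplan-Meier quartiles for OS and rates at 12, 16, 20 and 24 weeks, by dose cohort in escalation and by tumor-specific cohort in expansion. The output groups named in SAP Appendix 2 are escalation 3 mg, escalation 5 mg, Cohort A and combinations of them.

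**The text promises long follow-up.** Protocol 3.1.1 states: "Patients will be followed until death or study completion". Protocol 3.1.2 says the same for all expansion patients and refers the reader to Appendix A. SAP 2.1 adds a definition: "Patients will be followed until death or study completion, which is defined as the CRF form" for end of study is filled in.

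**The schedule does not deliver it.** In Appendix A the only entry in the follow-up column is the survival row. Its footnote 17 opens "For subjects in Expansion Cohorts B, C, D, and E" and then sets telephone contact every 12 (±2) weeks, with recording of subsequent anti-tumor therapy, later tumor results in patients who stopped without progression, and the date and cause of death. SAP Appendix 1 reproduces the footnote unchanged. For everyone else the last scheduled visit is treatment completion, "30 (±7) days after permanent treatment discontinuation".

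**The concern.** A site working from the schedule of events has no instruction to contact an escalation or Cohort A patient for survival after the treatment completion visit. The general sentence about follow-up gives no interval, method or data item.

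A survivor with no later contact would be censored near that visit. Progression is the first listed reason for ending treatment (protocol 3.6), so such censoring would often fall just after progression, when the risk of death has risen. It would then be informative. The Kaplan-Meier method treats censored patients as having the same later risk as those still observed, who would mostly be patients still on drug. The OS curve, median and fixed-week rates for these groups would therefore tend to be too high.

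Subsequent therapy is affected too. SAP 13.2 summarizes it for each cohort in each phase, but its only scheduled collection after the completion visit is in footnote 17.

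**Working it through.** **1. Who is affected.** Protocol 3.2 gives 12 escalation patients and expansion cohorts of 6, 40, 40, 15 and 15.

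- Plan's own totals: 6 + 40 + 40 + 15 + 15 = 116, and 12 + 116 = 128. Both are reproduced.
- Inside footnote 17: 40 + 40 + 15 + 15 = 110, and 110/128 = 85.9%.
- Outside footnote 17: 12 + 6 = 18, and 18/128 = 14.1%.

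**2. When scheduled contact ends for the 18.** The window is 30 − 7 = 23 to 30 + 7 = 37 days after permanent discontinuation.

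**3. Does the text override the schedule?**

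| Place | Who | Follow-up |
|---|---|---|
| Protocol 3.1.1; SAP 2.1 | Escalation | To death or study completion |
| Protocol 3.1.2; SAP 2.2 | Cohorts A–E | To death or study completion; the protocol points to Appendix A |
| Appendix A footnote 17; SAP Appendix 1 | Cohorts B–E | Calls every 12 (±2) weeks |
| Appendix A, treatment completion | All | One visit, day 23–37 |

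For Cohort A, 3.1.2 sends the reader to the schedule that leaves Cohort A out. Protocol 6.5 uses study completion in the title of the 30-day visit, and SAP 2.1 ties completion to a form. A site could therefore complete that form after the 30-day visit and believe it had met 3.1.1. The text states an intention but does not close the gap.

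**4. Scale if contact did end at that visit (illustration only).** Protocol 1.3.3 gives fruquintinib medians from the phase 3 colorectal study: PFS 3.71 months and OS 9.30 months. Assume exponential time to stopping drug, with rate λ1 = ln 2/3.71 = 0.187 per month, followed by independent exponential survival with rate λ2. Choose λ2 so that S(t) = (λ2·e^(−λ1·t) − λ1·e^(−λ2·t))/(λ2 − λ1) equals 0.5 at the OS median. The share of post-treatment deaths within d days is 1 − exp(−λ2·d/30.4375).

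For an OS median of 9.30, the post-treatment median is 3.97 months and λ2 = ln 2/3.97 = 0.174. At d = 30 the share is 1 − exp(−0.174 × 0.986) = 15.8%.

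| OS median (months) | Post-treatment median (months) | d = 23 | d = 30 | d = 37 |
|---|---|---|---|---|
| 6.57 (placebo arm, low case) | 1.85 | 24.6% | 30.8% | 36.5% |
| 9.30 | 3.97 | 12.3% | 15.8% | 19.1% |
| 12 (assumed, high case) | 6.36 | 7.9% | 10.2% | 12.4% |

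Under these assumptions, most deaths after treatment would fall beyond the last scheduled visit.

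**The case against.** The strongest reply is that nothing in the plan orders early censoring. Three protocol and SAP statements require follow-up to death or study completion. Protocol 8.5 censors OS at the date last known alive, and SAP 16.1.6 uses the last follow-up date or the end-of-study date; neither sets a cut-off after treatment. The Amendment 4 entry "Added survival follow-up of patients" lists Section 3.1.1 among the places changed, which suggests escalation patients were meant to be covered. This stands, and it is why the point is a contradiction to reconcile and not a flawed censoring rule.

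Contact need not stop entirely at day 30. Protocol 6.4 continues efficacy follow-up in patients who stop without progression, 7.3 follows unresolved adverse events, and 7.1.4 keeps drug-related serious events reportable. Deaths in the adverse event reporting period are recorded for all patients (7.1.8.5). These can update the last-known-alive date, but they are not a survival schedule, and 6.4 again defers to Appendix A.

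Short follow-up would also be visible: SAP 16.2 summarizes duration of survival follow-up, and SAP 8.2 counts patients who enter it. That reveals the problem but does not remove bias.

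Finally, the stakes are modest. SAP 5.5 plans no hypothesis tests, and OS medians in groups of about 6 would be imprecise even with complete follow-up. This limits the weight of the point but does not answer it.

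**Conclusion.** The point holds as an internal contradiction affecting about 18 of 128 planned patients. OS is to be estimated for escalation and Cohort A, the text requires long follow-up, and the only operational survival instruction leaves them out. If the schedule is what sites follow, the OS curves for these groups would be informatively censored and would tend to be too high.

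A reader might infer more: that OS in these patients is censored at about a month by design, that nearly all survivors would be lost then, or that the curves would reflect little beyond deaths on treatment. The documents do not support this. The body text and the last-known-alive rule point the other way, other contacts are possible, and treatment may continue past progression (protocol 3.6), so the completion visit need not fall close to progression.

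The percentages above show scale only. They apply colorectal medians to patients with mixed tumors, treat every PFS event as the point of stopping drug, and assume no later contact. If the text is followed instead, the loss does not arise. The escalation primary endpoint (DLT incidence) and the PFS rates with a named week in protocol 8.5 (Cohorts B–E) do not depend on this.

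**What to change.** Reconcile protocol 3.1.1 and 3.1.2 with Appendix A footnote 17, and SAP 2.1 and 2.2 with SAP Appendix 1. The simplest route is to extend footnote 17, in both documents, to escalation and Cohort A patients who can still be reached. Scheduled coverage would rise from 110 to 128 planned patients, with the same items collected as for Cohorts B–E. SAP 2.1 should also state that the 30-day visit alone does not constitute study completion for a living patient who has not withdrawn.

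Where this follow-up was not or cannot be obtained, add a sentence to SAP 16.2 replacing Kaplan-Meier OS for these groups with a listing of deaths and last-known-alive dates. This may well be needed: Appendix K shows that the RP2D had already been set by Amendment 3, before Amendment 4 added survival follow-up, so some of these patients may have left the study. The documents do not say whether they can be recontacted.

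The cost is telephone contacts for at most 18 patients, fewer if some cannot be reached, or the loss of an imprecise descriptive estimate in small groups. No sample size changes.
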